### 5.1 Informed Consent Process

The Principal Investigator or his/her authorized designee will conduct the Informed Consent Process, as required by applicable regulations and the center's IRB/EC. This process will include a verbal discussion with the subject on all aspects of the clinical investigation that are relevant to the subject's decision to participate, such as details of clinical investigation procedures, anticipated benefits, and potential risks of clinical investigation participation. During the discussion, the Principal Investigator or his/her authorized designee will avoid any improper influence on the subject and will respect subject's legal rights. The subject shall be provided with the informed consent form written in a language that is understandable to the subject and has been approved by the center's IRB/EC. The subject shall have adequate time to review, ask questions and consider participation.

If the subject agrees to participate, the Informed Consent form must be signed and dated by the subject and by the person obtaining the consent. The signed original will be filed in the subject's hospital or research charts, and a copy will be provided to the subject.

The Principal Investigator or his/her authorized designee will document the informed consent process in the subject's hospital and/or research charts. The date of signature will be entered on an applicable Case Report Form (CRF).

Failure to obtain informed consent from a subject prior to clinical investigation enrollment should be reported to Sponsor within 5 working days and to the reviewing center's IRB/EC according to the IRB's/ EC's reporting requirements.

If, during the clinical investigation, new information becomes available that can significantly affect a subject's future health and medical care, the Principal Investigator or his/her authorized designee will provide this information to the subject. If relevant, the subject will be asked to confirm their continuing informed consent in writing.

## 5.2 Screening

The Principal Investigator or delegated study personnel is responsible for screening all potential patients to determine patient eligibility for the clinical investigation.

If a patient meets all inclusion criteria and does not meet any of the exclusion criteria, he/she is eligible for the clinical investigation.

Records of patients who are screened must be maintained.

In case the subject does not meet all inclusion criteria or meets any of the exclusion criteria, the subject is considered a screening failure. The Principal Investigator or the delegated study personnel will record the screening failure in the hospital records and on a screening log as required.

## 5.3 Point of Enrollment

Patients are considered enrolled in the clinical investigation and become subjects from the moment the patients have provided written Patient Informed Consent.

The Principal Investigator or delegated study personnel will record enrollment information (name of the clinical investigation, date of consent and Inclusion/exclusion information) in the hospital records and complete and submit an applicable CRF in a timely manner.

Notification of enrollment to the Sponsor is considered to have occurred when the Sponsor has received the applicable CRF.

## 5.4 Scheduled Procedures

The Principal Investigator is responsible for ensuring all clinical investigation data are collected as required per CIP scheduled procedures.

The list of clinical investigation specific tests and procedures (Table 2) below summarize visit flow and requirements of this clinical investigation.

Table 2: List of all clinical investigation specific tests and procedures

Visit	Enrollment / Baseline	Trial System Implant (Initial Trial Evaluation Period Start)	End of Initial Trial Evaluation Period Begin Extended Trial Evaluation (if applicable)	End of Extended Trial Evaluation Period (if applicable)	Unscheduled Visit
Study Activity					
Informed Consent	X				
Subject Eligibility	X				
Demographics, Pain History & Diagnosis	X				
Numerical Rating Scale	X		X	(X)	

PROMIS-29	X				
Pain Catastrophizing Scale	X				
Patient satisfaction and PRP			X	(X)	
Randomization	X	(X)			
Implant procedure and system data		X			
Patient Trial Diary		X	X	(X)	
Email Programming Details		X	X	(X)	(X)
Stimulation Assessment		X	X	(X)	(X)
Qualify for permanent implant			X	(X)	
Reason for Visit					X
Procedure Time		X			
Programming Time		X			(X)
Subject's Feedback			X		
Clinician Assessment		X			
Physician's Preference			X*		
Imaging		X	X	(X)	(X)
Lead Location		X	X	(X)	(X)
SADEs, SAEs ADEs		(X)	(X)	(X)	(X)
Deviation(s)	(X)	(X)	(X)	(X)	(X)
Withdrawal	(X)	(X)	(X)	(X)	(X)
Death	(X)	(X)	(X)	(X)	(X)

(X) If applicable

\* only after last subject's last End of Initial Trial Period Visit- for a single site

#### 5.4.1 Enrollment/Baseline Visit

The following assessments and information will be collected at the baseline visit:

- Demographics, pain history, pain diagnosis
- Numerical Rating Scale (NRS)
- Patient Reported Outcomes Measurement Information System-29 (PROMIS-29)
- Pain Catastrophizing Scale (PCS)
- Deviations (if applicable)
- Withdrawal (if applicable)
- Death (if applicable)

#### 5.4.2 Randomization and Blinding

Randomization may occur at the end of the baseline visit or just prior to surgery for trial system implant (Initial Trial Evaluation Period Start) Visit.

Subjects will be randomized (1:1) using random permuted blocks of varying length and stratified by site. Subjects will be blinded to treatment group and treated in two groups as follows:

1. Group 1 (AB): anatomic lead placement followed by BurstDR™ stimulation during initial trial evaluation period
2. Group 2 (TB): targeted lead placement followed by BurstDR™ stimulation during initial trial evaluation period

Randomization assignment will be communicated to the site via the Randomization Application available in the EDC Site Portal.

Regardless of sedation, subjects will not be able to distinguish what implant technique (anatomic or targeted) is utilized without intimate knowledge of SCS programming, and with standardizing subject

interactions, the subjects will remain blinded to the treatment group. Implanting physicians and surgical support staff must follow the specific guidelines for the lead placement techniques and therefore cannot be blinded, but will be provided with a standardized script to assist with subject interaction as a way to minimize the risk of disclosing randomization assignments. Additionally, sites will be instructed to schedule study visits to restrict study subjects from being in the clinic at the same time, which aims to minimize subject to subject communication. Prior to study exit and before being unblinded, subjects will be asked about their memory for intra-operative testing as an assessment of the blind. Intra-operative testing is the key distinguishing feature between the techniques, so assessment of memory for experience will help to establish the status of the blind for each subject.

A Blinding Plan will be maintained separately which will include a listing of all parties involved in the study to manage workflow and identification of blinded and unblinded information.

[figure not shown]
#### **5.4.3 Trial System Implant (Initial Trial Evaluation Period Start)**

Record the required information on the applicable CRF:

- Implant procedure and system data
- Stimulation assessment
- Clinician assessment
- Procedure time
- Programming time
- Adverse events (if applicable)
- Deviations (if applicable)
- Withdrawal (if applicable)
- Death (if applicable)

Upload and attach the following documentation to the applicable CRF:

- Images

The subject will complete a Patient Trial Diary once a day utilizing an application located on the Patient Controller during the trial evaluation period. The subject will record areas of pain, stimulation therapy goals and percentage of pain relief in the diary. At the end of the trial evaluation period, the End of Trial Summary report will be submitted to the sponsor.

The following section of the protocol provides a guideline for surgical implantation and programming of the trial evaluation system.

#### **Lead Placement Technique:**

##### ***Anatomic lead placement (Randomization Group 1)***

Physicians may implant one or two leads as per their preference/standard of care at the site. Guidance for placement of the leads is provided below:

##### ***Placement of 1 lead:***

- Lead 1 – Place lead tip at the rostral end of T8 segment
- No tonic mapping/confirmation required
- Confirm position using fluoroscopy (X-ray) and reposition lead if needed

Placement of 2 leads:

- Lead 1 – Place lead tip at the rostral end of T8 segment
- Lead 2 – Place lead tip at the rostral end of T9 segment
- No tonic mapping/confirmation required
- Confirm position using fluoroscopy (X-ray) and reposition lead if needed

**Targeted Lead Placement Technique (Randomization Group 2)**

- Physicians may implant one or two leads as per their preference/standard of care at the site
- Utilize the standard lead placement technique as per standard of care for BurstDR stimulation.
- Position lead(s) at the appropriate thoracic segment in the epidural space – dictated by pain coverage required by patient
- Confirm adequate coverage of pain areas using tonic stimulation
- Adjust lead position as needed to attain adequate coverage of pain areas

**Anchoring Technique:**

Securing the SCS leads during this investigation is critical to evaluate the anatomic versus targeted lead placement through the course of the trial period. Acceptable methods to secure the leads include suturing and utilization of anchors. Methods that are not allowed during this investigation include include steri-strips and pre-manufactured bandages.

**Postoperative Programming:**

After the trial system implant procedure is complete, all subjects will be programmed with BurstDR™ stimulation programs by trained personnel and/or an Abbott representative using the Clinician Programmer. Subjects will be given a Patient Controller and instructed how to use the Patient Controller to adjust stimulation as needed to produce the best results and to complete the Patient Trial Diary daily during the trial evaluation period

During the initial trial evaluation period, the stimulation parameters may be optimized. If this is needed, the subject would return to the clinic for adjustments to the programming parameters. Study personnel performing programming activities will utilize the same methods as the post-op programming to ensure the subject remains blinded to treatment group. This visit should be documented as an unscheduled visit. If a lead revision is needed during the trial period, the subject should be withdrawn from the study.

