## **5.10 Subject Withdrawal**

Subjects must be informed about their right to withdraw from the clinical investigation at any time and for any reason without sanction, penalty or loss of benefits to which the subject is otherwise entitled. Withdrawal from the clinical investigation will not jeopardize their future medical care or relationship with the investigator. Subjects will be requested to specify the reason for the request to withdraw. The investigator must make all reasonable efforts to retain the subject in the clinical investigation until completion of the clinical investigation.

Examples of reasons for subject’s withdrawal include, but are not limited to:

- Subject and/or family request to withdraw consent
- Subject death
- Unsuccessful trial implant resulting in ineffective stimulation
- Lead revision
- System explant

The status of the subject’s condition should be documented at the time of withdrawal.

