### 6.1 Hypotheses

#### 6.1.1 Primary Endpoint Hypothesis

The primary endpoint is intended to demonstrate non-inferiority of the qualification rate at the end of the initial trial evaluation period for Group 1 (AB) compared to Group 2 (TB).

For each randomization group, the qualification rate is defined as the number of subjects who are identified as "qualified for permanent system implant" divided by total subjects who complete the initial trial evaluation period for the respective randomized group.

Qualification for permanent system implant is defined by a composite in which a subject meets all of the following conditions:

- >50% patient reported pain relief (PRP) at the end of the trial evaluation period
- Trial evaluation period lasted for a minimum of 3 days
- Physician recommends subject for permanent system implant
- Subject reports a willingness to pursue a permanent system implant
- 

Subjects are not qualified for permanent system implant if they meet both of the following:

- ≤50% PRP at the end of the trial evaluation
- Trial evaluation period lasted for a minimum of 5 days

Hypothesis:

The hypothesis is formally addressed as:

$$H_0: P_{AB} - P_{TB} \leq -15\%$$

[figure not shown]
$$H_1: P_{AB} - P_{TB} > -15\%$$

where

[figure not shown]
$P_{AB}$  = permanent system qualification rate of Group 1 (AB)

$P_{TB}$  = permanent system qualification rate of Group 2 (TB)

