#### 6.1.1.1 Analysis Methodology

#### 6.1.1.2 Sample Size Determination

#### 6.1.1.3 Analysis Populations

The analysis population includes subjects who are randomized and either qualify for a permanent system implant or do not qualify for a permanent system implant, as defined earlier.

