#### 6.1.1.5 Missing Data

A sensitivity analysis will be carried in the same manner as the primary analysis, except the subjects who were randomized, underwent the trial system implant and did not complete the initial trial period will be included in the analysis and be treated as non-qualified subjects.

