The primary marker of success during the typical SCS trial evaluation period is qualification for permanent implant. Qualification per standard of care for SCS devices includes a successful trial evaluation period defined by subject's assessment of 50% or more pain relief during the trial evaluation, physician's recommendation, and the subject's willingness to continue to the permanent system. As such, the current clinical investigation defines qualification for permanent implant as a composite endpoint based upon standard of care to be used as for the primary endpoint. Demonstration of non-inferiority will establish that the anatomic placement technique is similar to traditional, targeted techniques in terms of subject selection for permanent implant. Secondary and descriptive endpoints will provide evidence of the physician and patient experience with both types of implant procedures and with the Invisible Trial System, overall.

As the primary hypothesis will be tested prior to actual permanent implant status, the clinical investigation will end at the qualification stage without consideration of the actual permanent implant status for subjects. Qualification based on efficacy, subject self-selection, and physician discretion is sufficient to make inferences about the anatomic procedure and Invisible Trial System features.

Failure to qualify for this study is contingent upon a minimum of 5 days of stimulation. Anecdotal reports indicated that burst stimulation may take up to 5 days to impart full benefit; whereas, tonic stimulation does not historically have a wash-in period to reach full benefit. As such, failures occurring before 5 days may be a product of insufficient exposure to burst therapy, and the primary endpoint is contingent upon equitable treatment between randomization arms in all other aspects excepting procedure. Additionally, subjects who fail the burst trial and proceed to an extended trial evaluation with tonic stimulation will need to ensure that they are provided sufficient time to assess the alternate stimulation mode. At present, the wash-out period for burst, if any, has not been established but is suspected to be at least a few hours and up to 2 days. As such, subject's ending their trial evaluation before 5 days without meeting criteria for qualification for permanent implant will be considered a deviation and treated as missing data. Use of this criterion will also

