## 6.7 Success Criteria

The clinical investigation will be considered a success when the primary endpoint is met.

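### Subjects withdrawn for lead revision or other early exit leave the primary completer analysis, and the visible text gives the planned analysis that counts them as failures no role in declaring non-inferiority

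*Combined protocol and SAP*

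**What the plan says.** Under Postoperative Programming in section 5.4.3: "If a lead revision is needed during the trial period, the subject should be withdrawn from the study". Section 5.10 gives examples of withdrawal reasons, among them lead revision, system explant and "Unsuccessful trial implant resulting in ineffective stimulation".

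The primary qualification rate in section 6.1.1 is the number qualified "divided by total subjects who complete the initial trial evaluation period". Section 6.1.1.3 limits the population to randomized subjects who "either qualify for a permanent system implant or do not qualify for a permanent system implant, as defined earlier". Being not qualified needs both PRP of 50% or less and at least 5 days of evaluation (sections 4.3.1 and 6.1.1). Under section 6.2, a subject who stops before day 5 without qualifying "will be considered a deviation and treated as missing data". The reason given is that "failures occurring before 5 days may be a product of insufficient exposure to burst therapy".

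Section 6.1.1.5 plans a sensitivity analysis run like the primary one, "except the subjects who were randomized, underwent the trial system implant and did not complete the initial trial period" are added as non-qualified. Section 6.7 reads: "The clinical investigation will be considered a success when the primary endpoint is met". The visible text does not mention the sensitivity analysis again.

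**The concern.** Lead position is what the trial randomizes. Section 2 explains that tonic feedback is used to check that leads sit correctly. The targeted arm confirms coverage this way and adjusts the leads, whereas the anatomic arm is not required to (section 5.4.3). A lead revision or ineffective stimulation can therefore be a result of the assigned technique, and implanters know the assignment (section 5.4.2). Yet a subject who leaves for this reason before completing the initial period is removed from the primary comparison. The burst-exposure argument in section 6.2 explains why an early lack of relief is not called a failure. It does not explain why a lead revision is left out.

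If technique-related withdrawals are more frequent with anatomic placement, the completers in that arm are a favourably selected group, and the trial could declare non-inferiority when the technique is 15 points worse. The visible text also does not say what is concluded if the completer analysis meets the margin and the section 6.1.1.5 analysis does not.

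**Working it through.** The public copy shows no sample size, alpha, expected rate or withdrawal allowance, so there is no plan figure to reproduce. Only the -15 point margin and the 1:1 allocation come from the documents.

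**Assumed inputs.** 160 randomized and implanted per arm; one-sided 2.5%; 65% of targeted completers qualify; Wald test with unpooled standard error. Let w be the withdrawal share in an arm, c its completer rate, and f the share of withdrawals that are technique failures. The other withdrawals would have qualified at rate c.

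**Formulas** (A anatomic, B targeted)

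- True rate in an arm: r = c(1 - f·w).
- At the margin: rA = rB - 0.15, so cA = rA/(1 - f·wA), with cB = 0.65.
- SE = sqrt[cA(1 - cA)/(160(1 - wA)) + cB(1 - cB)/(160(1 - wB))].
- False success of the completer test = Phi((cA - cB + 0.15)/SE - 1.96).

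**One case in full** (10% vs 3% withdrawal, f = 1). rB = 0.65 × 0.97 = 0.6305. rA = 0.4805. cA = 0.4805/0.90 = 0.5339. SE = sqrt(0.5339 × 0.4661/144 + 0.65 × 0.35/155.2) = 0.0565. (0.5339 - 0.65 + 0.15)/0.0565 = 0.60. Phi(0.60 - 1.96) = 8.7%.

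**False success of the completer analysis**

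| Withdrawal, anatomic vs targeted | f = 0 | f = 0.5 | f = 1 |
|---|---|---|---|
| 5% vs 5% | 2.5% | 2.1% | 1.8% |
| 5% vs 3% | 2.5% | 2.8% | 3.2% |
| 10% vs 3% | 2.5% | 4.7% | 8.7% |
| 15% vs 3% | 2.5% | 7.5% | 20.6% |
| 3% vs 10% | 2.5% | 0.8% | 0.2% |

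At 10% vs 3%, the range for f = 0.5 to 1 is 4.1% to 6.9% with 100 per arm and 5.4% to 11.3% with 250 per arm.

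**Section 6.1.1.5 analysis alone.** The rates become (1 - w)c with n = 160. If no withdrawal is technique-related (f = 0, cA = 0.50), 5% vs 5% gives 0.475 against 0.6175, a difference of -0.1425. With SE = 0.0551, Phi(0.0075/0.0551 - 1.96) = 3.4%. The same steps give 4.6% at 10% vs 10% and 14.5% at 3% vs 10%. Used alone, this analysis has its own error.

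**Both required** (simulation, 400,000 runs per case, 160 per arm). For f = 0.5 and 1, false success is 1.8% and 2.1% at 5% vs 3%, 1.1% and 2.4% at 10% vs 3%, and 0.6% and 2.4% at 15% vs 3%. For f = 0 it is 2.1% at 5% vs 5% and at 10% vs 10%, and about 2.4% at 3% vs 10%. With 100 per arm the largest value is 2.7%, a small-sample effect of the Wald test.

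**How often the two disagree.** With equal completer rates of 65% and withdrawal of 10% vs 3%, about 30% of simulated trials pass on completers and fail under section 6.1.1.5.

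**The case against.** The plan has not overlooked these subjects. Section 6.1.1.5 pre-specifies the stricter analysis. Section 6.2 classes early exits as missing data, so their place under section 6.1.1.5, headed Missing Data, is nearly explicit. Lead problems are also guarded against: the anatomic arm requires fluoroscopic confirmation with repositioning if needed, section 5.4.3 requires sutures or anchors, and meaningful migrations are reported by arm (section 4.3.3). The initial period can be as short as 3 days, and no document figure points to a 12-point withdrawal imbalance. Making a sensitivity analysis a condition of success also counts as failures, in one of the two tests, some subjects whom section 6.2 deliberately declines to call failures. With a small imbalance the harm is slight (2.8% to 3.2% against 2.5%), while the power lost is not.

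Much of this stands and limits the size of the point. The safeguards may keep revisions few, but they do not say how a subject who needs one enters the decision. Reporting migrations descriptively does not change the non-inferiority test. The burst-exposure reason still does not reach lead revision.

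A reader might infer that the exclusions favour anatomic placement, or that the trial's false-success rate is about 20%. The documents support neither. They give no withdrawal rates, and the 20.6% needs both 15% vs 3% withdrawal and every withdrawal being a technique failure.

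**Conclusion.** The gap is real on the visible text and should be fixed; confidence is medium. Withdrawals that may result from the randomized technique leave the primary comparison, and the planned analysis that brings them back has no stated role in success. Completer false success exceeds 2.5% only if technique-related withdrawal is more frequent in the anatomic arm. It is modest at a 2-point imbalance and material at 7 points or more. With equal withdrawal, withdrawal unrelated to technique, or an excess in the targeted arm, it is at or below 2.5%. All of these sizes rest on the assumed inputs.

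Two limits apply. Sections 6.1.1.1, 6.1.1.2 and 6.4 are headings without text in the public copy, so it cannot be said that the full plan lacks a rule. The text also leaves unclear how a subject is classed who needs a revision after day 5 with PRP of 50% or less: the not-qualified definition could cover this subject, while the withdrawal rule and the completer denominator point to exclusion. Subjects who complete at least 5 days with PRP of 50% or less do count as failures, so it would be wrong to read the plan as dropping treatment failures in general.

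**What to change.** In sections 6.7 and 6.1.1.5, require both the completer analysis and the section 6.1.1.5 analysis to meet the -15 point margin before non-inferiority is declared. Do not make the section 6.1.1.5 analysis the sole primary. State in section 6.1.1.5 that exits before day 5 without qualification are counted there. Report withdrawals by arm and reason. If section 6.1.1.1 of the full document already has such a rule, refer to it in section 6.7.

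This is a text change before analysis. Clinical handling and visits stay as they are. The cost is power, shown here on the same assumptions with 65% of completers qualifying in both arms:

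| Withdrawal, anatomic vs targeted | Both required | Completers alone |
|---|---|---|
| 5% vs 5% | 75% | 78% |
| 10% vs 10% | 72% | 76% |
| 5% vs 3% | 71% | 79% |
| 10% vs 3% | 48% | 78% |
| 15% vs 3% | 25% | 76% |

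The large losses are not always deserved. With equal completer rates the true difference is -0.65 × f × (wA - wB). At 10% vs 3% that is -4.6 points if all withdrawals are technique failures, -2.3 if half are and 0 if none are, yet power is 48% in each case. The planned power should be restated on this basis so that the sponsor accepts the cost knowingly. No larger enrolment is requested.
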